8.3.3 TRIAL STOPPING RULES

Dosing and/or recruitment will be interrupted until the SRC has completed a thorough review of all available data, for any of the following reasons, but not limited to:

• If 1 subject experiences an SAE

Clinical trial stopping rules:

- If 2 RVP-001 related SAEs occur in a cohort
- If 2 subjects experience severe RVP-001 related AEs
- Occurrence of an RVP-001 related AE or SAE which results in death

Relatedness to study drug will be determined by the investigator.

If the study is halted, the IRB will be notified. The study may be resumed or terminated; however, it will not be resumed until a further notice to resume the study is submitted and approved by the IRB.

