8.3.2 COHORT STOPPING RULES

If any of the following safety concerns are observed, dosing of all subjects at the given dose level or higher will be suspended/halted and all available data will be evaluated by the Safety Review Committee (SRC).

- 1) If one (1) RVP-001-related SAE occurs in a cohort
- 2) Moderate or severe AEs in 50% of the subjects in the cohort or more
- Clinically significant laboratory abnormalities of the same character in 3 or more subjects (e.g., ALT >3 ULN)
- Clinically significant changes in vital signs of the same character in 3 or more subjects: BP consistently greater than 160 mmHg associated with an increase from baseline greater than 20 mmHg
- 5) Clinically significant changes in ECGs of the same character in 3 or more subjects: QTcF greater than 480 msec with an increase from baseline greater than 60 msec

Dose continuation (remaining subjects within a cohort or remaining dosing for a subject) or escalation decision will be made following evaluation of the event by the SRC.

Prior to starting a new dose/cohort, dose escalation will be discussed during the SRC meeting and may be modified or stopped depending on the investigator's or sponsor's decision, based on but not limited to the following:

- 1) New clinically significant abnormalities in physical examination, 12-lead ECG or vital signs in 2 or more subjects
- 2) Overall pattern of clinical changes or symptoms that may have appeared minor in terms of an individual AE or subject, but which collectively present a safety concern
- 3) Clinically significant changes in organ-specific laboratory parameters (e.g., liver function enzymes, renal function studies in one or more subjects)
- 4) Pattern of laboratory changes (e.g., a consistent increase or decrease within 2 or more subjects or within or across dosing groups) which might indicate an overall safety concern

In the event that a cohort is stopped due to non-drug-related events, a new cohort of additional subjects may be enrolled to replace the stopped cohort.

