9.10.2 DEFINITION OF A SERIOUS ADVERSE EVENT (SAE)

A SAE is any AE that at any dose:

- Results in death
- Is life-threatening (i.e., in the opinion of the principal investigator (PI) the subject is at immediate risk of death from the AE)
- Requires inpatient hospitalization or prolongation of existing hospitalization
- Results in persistent or significant disability/incapacity (a substantial disruption of the subject's ability to conduct normal life functions)
- Results in a congenital anomaly/birth defect
- Constitutes an important medical event:
 - These may not result in death, be life-threatening, or require hospitalization, but may be considered serious when they jeopardize the health of the subject and require medical or surgical intervention to prevent one of the outcomes listed.
 - Any other event (e.g., allergic bronchospasm requiring intensive treatment in an emergency room or at home, blood dyscrasias, convulsions that do not result in inpatient hospitalization, or the development of drug dependency or drug abuse) thought to be serious by the Principal Investigator

Version 2.0: 9 May 2022 Confidential Page 59

Events not considered to be serious are hospitalizations that:

- Were planned before entry into the clinical trial
- Are for elective treatment of a condition unrelated to the studied indication or its treatment
- Occur on an emergency outpatient basis and do not result in admission (unless fulfilling other criteria above)
- Are parts of the normal treatment or monitoring of the studied indication and are not associated with any deterioration in condition

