9.10.4 RECORDING OF ADVERSE EVENTS

AEs will be recorded and evaluated for their seriousness, severity, and relationship to the study treatment. AEs will be collected and documented from the time of providing written informed consent (screening) until 7 days after study drug administration. Subjects will be asked to self-report between day 8 (follow up call) and day 30 following drug administration. If emerging or ongoing AEs are reported at the follow-up phone call or after follow-up, additional visits and phone calls will be arranged as unscheduled visits. During each study visit the subject will be questioned directly regarding the occurrence of any adverse medical event according to the schedule in eCRF. All AEs, whether ascribed to study procedures or not, will be documented immediately in the subject's eCRF. AEs will be followed-up until complete resolution, or until the Investigator judges it safe to discontinue follow-up. The relationship to the study medication will be classified according to the categories described in Section 9.10.6. Classification of AEs will be performed by System Organ Class (SOC) and Preferred Term (PT) using the Medical Dictionary for Regulatory Activities (MedDRA), version 24.0 or higher.

Concomitant medications will be coded using the World Health Organization drug dictionary (WHO-DDE March 2021 or later).

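### The related-SAE stopping rule in Section 8.3.3 counts within one cohort only, so related SAEs in different cohorts can meet none of the three listed trial stopping rules: a narrow gap, cheaply closed

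*Combined protocol and SAP*

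**What the plan says.** Section 8.3.3 of the protocol has two tiers. In the first, dosing and/or recruitment is interrupted until the SRC has finished its review, for reasons that include "If 1 subject experiences an SAE". In the second, a list labelled as the clinical trial stopping rules has three items:

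- "If 2 RVP-001 related SAEs occur in a cohort"
- "If 2 subjects experience severe RVP-001 related AEs"
- a related event that results in death.

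The section closes by saying that if the study is halted the IRB is notified, and "it will not be resumed until a further notice to resume the study is submitted and approved by the IRB".

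Section 8.3.2 sets the cohort rules. After one related SAE in a cohort, "dosing of all subjects at the given dose level or higher will be suspended/halted" and the SRC evaluates the data. The SRC then decides on continuation or escalation.

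On how events are rated, Section 9.10.4 says "AEs will be recorded and evaluated for their seriousness, severity, and relationship to the study treatment". Section 9.10.2 lets an important medical event count as serious without hospitalization, including any other event "thought to be serious by the Principal Investigator". Severity follows CTCAE version 5.0 (Section 9.10.5, Table 6).

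**The concern.** The two neighbouring rules count differently. Severe related AEs are counted by subject across the trial. Related SAEs are counted by event within one cohort. One consequence is an odd ordering: two severe but non-serious related AEs at two dose levels stop the trial, while two related SAEs at those levels may not. Another is that one subject with two related SAEs meets the SAE rule, while two subjects with one each in different cohorts do not.

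This is a first-in-human ascending-dose study whose primary objective is safety. Related SAEs that recur as the dose changes are evidence a trial-level rule would be expected to count. Without a count, the decision to go on rests with the SRC, whose stated minimum membership is the Principal Investigator and the sponsor's medical personnel (Section 9.12.2). A trial halt clearly adds IRB approval before dosing resumes. Section 8.3.2 already asks the SRC to look at laboratory changes "within or across dosing groups", so a count across cohorts fits the protocol's own approach.

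**Working it through.** **Step 1: which combinations meet a rule.** Take two subjects, each with one related SAE. Let each of four features be yes or no: same cohort, first event severe, second event severe, a fatal outcome. That gives 16 combinations. As written, a stopping rule is met if the cohort is the same, or both events are severe, or there is a death. I read severe as Grade 3 or higher.

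- Met: 13 of 16.
- Not met: 3 of 16. These are different cohorts, non-fatal, with neither event severe, only the first severe, or only the second severe.
- With a count across all cohorts: 16 of 16 met.

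**Step 2: how the case could arise.** Seriousness and severity are rated separately (9.10.4), so an SAE below Grade 3 is possible. A second SAE in another cohort can occur if the SRC clears further dosing after the first (8.3.2), or if a late event in an earlier cohort is self-reported up to Day 30 (9.10.4).

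**Step 3: size.** The protocol gives no SAE rate and no figure to reproduce for this rule. Inputs from Section 5.1 and Table 1 are 4 cohorts with 6 active subjects each (24), plus an optional fifth (30). These inputs are assumed:

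- p is the related-SAE risk per active subject, equal at all doses and independent.
- Each subject has at most one related SAE, and none is fatal.
- q is the share of related SAEs graded severe.
- There are no other severe related AEs, and all planned active subjects are dosed.

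For one cohort of 6, the chance of no SAE is p0 = (1−p)^6 and of exactly one is p1 = 6p(1−p)^5. The gap is the event that no cohort has two, at least two cohorts have one, and at most one of those SAEs is severe:

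Gap = Σ over j = 2 to 4 of C(4,j) · p1^j · p0^(4−j) · P(Bin(j,q) ≤ 1)

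Worked for p = 0.02: p0 = 0.98^6 = 0.8858 and p1 = 6 × 0.02 × 0.98^5 = 0.1085. The terms for j = 2, 3, 4 before the severity factor are 0.05540, 0.00452 and 0.00014.

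- q = 0 (none severe): every factor is 1, so the gap is 0.05540 + 0.00452 + 0.00014 = 0.0601.
- q = 0.75: the factors are 0.4375, 0.1563 and 0.0508, so the gap is 0.02424 + 0.00071 + 0.00001 = 0.0249 (rounded from unrounded terms).
- q = 1: every factor is 0, so the gap is 0.

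Check against totals at q = 0: P(Bin(24, 0.02) ≥ 2) = 0.0826 with the trial-wide count and 0.0226 as written, a difference of 0.060.

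| p (assumed) | Two or more subjects with related SAEs | Gap, none severe | Gap, 75% severe | Gap, 90% severe | Gap, all severe |
|---|---|---|---|---|---|
| 1% | 2.4% | 1.8% | 0.8% | 0.3% | 0 |
| 2% | 8.3% | 6.0% | 2.5% | 1.1% | 0 |
| 5% | 33.9% | 21% | 8.2% | 3.4% | 0 |

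With the fifth cohort (5 in place of 4 in the formula), the none-severe figures become 2.9%, 9.2% and 29.3%; the all-severe figure stays 0.

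**The case against.** The strongest reply is that the first tier of 8.3.3 is already trial-wide. Any SAE in any cohort, whatever its relatedness or severity, interrupts dosing and/or recruitment. A second SAE triggers the same review again, with the first in view. If that interruption is itself read as a study halt, IRB approval to resume would already be required and only the stated count would be missing. This largely stands. The section does separate the interruption from the list it labels as stopping rules, so the reading is open.

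Other safeguards also stand:

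- Section 8.3.2 lets the SRC modify or stop escalation on an overall pattern of changes, with no cohort limit.
- Section 11.1.4 allows the study to be suspended for unacceptable risk, at discretion, with resumption once the sponsor, IRB and/or FDA are satisfied.
- SAEs go to the IRB within 24 hours (9.10.7). Unexpected serious reactions go to regulators within 7 or 15 days (9.10.8, 9.10.9), and the listed class events need an IND safety report (9.10.12).

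None of these is a mandatory count across cohorts.

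The scenario is also narrow. Table 6 puts hospitalization, disabling and medically significant events at Grade 3 and life-threatening events at Grade 4, so most SAEs would already count under the severe-AE rule. That stands, and it makes the none-severe column remote.

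Finally, counting by dose level and leaving patterns across levels to the SRC is a coherent design. The Data Safety Monitoring Plan and the safety plan, which are not among the documents, may hold a count. If so, 8.3.3 should state it.

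**Conclusion.** On the wording of Section 8.3.3, two subjects with non-fatal related SAEs in different cohorts, not both severe, meet none of the three listed trial stopping rules. No other section states a count across cohorts. What is missing is that count, and the IRB-approved restart that clearly follows a halt.

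A reader might infer that dosing could continue unreviewed while related SAEs accumulate. The documents do not support that: each SAE brings an interruption and SRC review, and each related SAE suspends its dose level and those above.

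A reader might also take the 24-subject figures as ceilings. They are not. The mandatory pauses, which the calculation ignores, would lower them, but the optional fifth cohort raises them. The rates, the equal risk across doses and the severe share are all assumptions. If 75–90% of related SAEs are severe, the gap is 0.3–0.8%, 1.1–2.5% or 3.4–8.2% at a risk of 1%, 2% or 5%.

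This is a minor point and a cheap improvement.

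**What to change.** Keep the existing related-SAE item in Section 8.3.3 and add to it: *or 2 or more subjects experience RVP-001 related SAEs across all cohorts*. It would also help to say whether the one-SAE interruption counts as a halt that needs IRB approval to resume.

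The change needs no extra procedures or subjects. Its cost is slightly more frequent trial halts, each needing IRB approval to resume, which 8.3.3 allows. Under the assumptions above, the added chance of meeting a two-event rule equals the gap. At a risk of 1%, 2% or 5% it is 0–1.8, 0–6.0 or 0–21 percentage points with 24 active subjects, and 0–2.9, 0–9.2 or 0–29.3 with 30. Some halts could come from SAEs in placebo subjects, because the investigator who judges relatedness is blinded (Sections 7.3 and 8.3.3). The figures count active subjects only and leave this out.

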8.4 LOST TO FOLLOW-UP

For subjects who are lost to follow-up (i.e., those subjects whose status is unclear because they fail to be available for study visits without stating an intention to withdraw), an investigator should show "due diligence" by documenting in the source documents steps taken to contact the subject, e.g., dates of telephone calls, registered letters, etc.

Version 2.0: 9 May 2022 Confidential Page 47

9 STUDY ASSESSMENTS AND PROCEDURES

9.1 SAFETY ASSESSMENTS

9.1.1 SAFETY MONITORING

Subjects will be monitored throughout the study by clinical site staff for AEs. A physician will be responsible for the clinical aspects of the study and will be available at all times during the study. If necessary, a physician, either at the clinical site or in a nearby hospital will administer treatment for any AE(s).

Additional non-invasive procedures that are already specified in the protocol may be performed, if it is believed that an important effect of the IP(s) is occurring or may occur at a time when no measurements are scheduled, or if extra procedures are needed in the interests of safety.

Additional blood samples, urine samples or other diagnostic tests for safety assessments may be taken if required by the investigator or sub-investigator at any point.

9.1.2 VITAL SIGNS

BP, respiratory rate, HR, and body temperature will be measured in a supine position (except for safety reasons) at the time points described in Section 3.2 (SOA). HR and pulse oximetry will be monitored continuously for 4 hours post dose.

Subject should be in supine position at least 5 minutes prior to measurements.

The acceptable deviations from the nominal vital signs measurement time points are:

- The pre-dose vital signs measurements will be taken ≤2 h before dosing.
- Post-dose vital signs measurements will be taken ± 2 min from the nominal post-dose time points for the first hour. Post-dose vital signs measurements will be taken ± 15 min from all other nominal post-dose time points.
- Discharge vital signs measurements will be taken ± 1 h from the nominal time point.

If a subject shows an abnormal assessment at any stage, repeat measurements may be made and the abnormality followed to resolution if required. Additional measurements may be taken as deemed necessary by the investigator or sub-investigator.

Any clinically significant abnormality, including changes from baseline, must be reported as an AE.

9.1.3 ECG MEASUREMENTS

Supine (single) 12-lead ECGs will be taken at 1, 3 and 8 minutes post dose after the subject has been in the supine position for a minimum of 5 min. Supine triplicate 12-lead ECGs (3 ECGs taken approximately 1 minute apart) after the subject has been in the supine position for a minimum of 5 min will be performed at the nominal timepoints in Section 3.2 (SoA). For triplicate ECGs, the mean of the three recordings will be reported.

- The pre-dose ECG measurements will be taken ≤2 h before dosing
- Post-dose single ECG measurements (minutes 1, 3 and 8) will be taken ± 2 min from the nominal post-dose time point
- All other ECGs will be taken ± 10 min for first 3 hours (excluding above) post dose and ± 30 min thereafter.
- Discharge ECG measurements will be taken ± 1 h from the nominal time point.

If a subject shows an abnormal assessment at any stage, repeat measurements may be made and the abnormality followed to resolution if required. Additional measurements may be taken as deemed necessary by the investigator or sub-investigator.

Any clinically significant abnormality, including changes from baseline, will be reported as an AE.

9.1.4 PHYSICAL EXAMINATION INCLUDING NEUROLOGICAL ASSESSMENT

A complete physical examination will be performed at admission. Height and body weight will be measured, and BMI will be calculated at screening. A complete physical examination includes assessments of the following: head, eyes, ears, nose, throat, neck, chest, lungs, abdomen, extremities, musculoskeletal, dermatological, CV/peripheral vascular, and neurological examination.

A complete neurological exam (including mental status exam, cranial nerves, coordination, and peripheral motor, sensory and reflex examinations of all extremities) will be performed as indicated in Section 3.2 (SoA).

If a subject reports or daily examination identifies any treatment emergent moderate or severe neurological signs/symptoms, a complete neurological examination will be performed.

Changes from baseline abnormalities will be recorded at each subsequent physical examination. New or worsened abnormalities should be recorded as AEs, if judged appropriate by the Principal Investigator or Medical Sub-Investigator.

9.1.5 DRUG, ALCOHOL AND COTININE SCREEN

A urine drug screen (Amphetamines [refers to a group of drugs that includes methamphetamine/MDMA {commonly known as Ecstasy}], Barbiturates, Benzodiazepines, Cocaine, Ethanol, Marijuana/Cannabis, Methadone, Morphine/Opiates, pH, Phencyclidine and Tricyclic Antidepressants) and an alcohol urine test and urine cotinine test will be performed at screening. A urine drug screen, alcohol test and cotinine test will also be performed at admission.

9.1.6 PREGNANCY TEST

A highly sensitive urine pregnancy test will be performed at screening for all female subjects. For WOCBP, a highly sensitive urine pregnancy test will also be performed before discharge. A highly sensitive serum pregnancy test will be performed at admission. The samples will be collected and processed as detailed in the clinical sample processing manual (CSPM).

9.1.7 FOLLICLE-STIMULATING HORMONE TEST

Serum FSH tests will be performed as detailed in Section 3.2 (SoA). The samples will be collected and processed according to the CSPM.

9.1.8 BODY WEIGHT, HEIGHT, AND BMI

The subject's body weight and height will be measured, and their BMI will be calculated according to the time schedule presented in Section 3.2 (SoA).

9.1.9 INJECTION SITE MONITORING

An assessment of each injection site will be made by a nurse, nurse practitioner, physician's assistant or physician according to the schedule in Section 3.2 (SoA).

The acceptable deviations from the nominal time points are:

 Post-dose (including discharge) examinations will be carried out ± 1 hour from the nominal post-dose time point

The injection site will be assessed and recorded according to the grading system in Table 4.

Table 4 Injection Site Examination

| PARAMETER | GRADE 1 MILD | GRADE 2 MODERATE | GRADE 3 SEVERE | GRADE 4 POTENTIALLY LIFE- THREATENING |
|-----------------------------------------------------------------------------------------------------------------------------------------------------------------------------------------------------------------------------------|--------------------------------------------------------------------------------------------------------------------------------------------------------------------------------|---------------------------------------------------------------------------------------------------------------------------------------------------------------------------------|---------------------------------------------------------------------------------------------------------------------------------------------------------------------------------------------------------------|--------------------------------------------------------------------------------------------------------------------------------------------------|
| Injection Site Pain or Tenderness Report only one | Pain or tenderness causing no or minimal limitation of use of limb | Pain or tenderness causing greater than minimal limitation of use of limb | Pain or tenderness causing inability to perform usual social & functional activities | Pain or tenderness causing inability to perform basic self-care function OR Hospitalization indicated |
| Injection Site Erythema or Redness ¹² Report only one > 15 years of age | 2.5 to < 5 cm in diameter OR 6.25 to < 25 cm ² surface area AND Symptoms causing no or minimal interference with usual social & functional activities | ≥ 5 to < 10 cm in diameter OR ≥ 25 to < 100 cm² surface area OR Symptoms causing greater than minimal interference with usual social & functional activities | ≥ 10 cm in diameter OR ≥ 100 cm² surface area OR Ulceration OR Secondary infection OR Phlebitis OR Sterile abscess OR Drainage OR Symptoms causing inability to perform usual social & functional activities | Potentially life- threatening consequences (e.g., abscess, exfoliative dermatitis, necrosis involving dermis or deeper tissue) |
| diameter with < 50% surface area of the extremity segment involved (e.g., upper arm or thigh) with < 50% surface area of the extremity segment involved (e.g., upper arm or thigh) OR UI OR Secondar infection OR Phlebitis OR | | ≥ 50% surface area of the extremity segment involved (e.g., upper arm or thigh) OR Ulceration OR Secondary infection OR Sterile abscess OR Drainage | Potentially life- threatening consequences (e.g., abscess, exfoliative dermatitis, necrosis involving dermis or deeper tissue) | |
| Injection Site Induration or Swelling Report only one > 15 years of age | Same as for Injection Site Erythema or Redness, > 15 years of age | Same as for Injection Site Erythema or Redness, > 15 years of age | Same as for Injection Site Erythema or Redness, > 15 years of age | Same as for Injection Site Erythema or Redness, > 15 years of age |
| ≤ 15 years of age | Same as for Injection Site Erythema or Redness, ≤ 15 years of age | Same as for Injection Site Erythema or Redness, ≤15 years of age | Same as for Injection Site Erythema or Redness, ≤ 15 years of age | Same as for Injection Site Erythema or Redness, ≤ 15 years of age |
| Injection Site Pruritus | Itching localized to the injection site that is relieved spontaneously or in < 48 hours of treatment | Itching beyond the injection site that is not generalized OR Itching localized to the injection site requiring ≥ 48 hours treatment | Generalized itching causing inability to perform usual social & functional activities | NA |

¹² Injection Site Erythema or Redness should be evaluated and graded using the greatest single diameter or measured surface area.

NA = not applicable

